8.2 COHORTS D- E

With amendment F, one additional cohort of N=10 patients will be added to explore the immune effects of combining tremelimumab with cryoablation (Cohorts D) and one cohort with RFA in a BTC population. Thus, there will be 2 new cohorts added at this time for a total of 20 additional patients. Results to date from cohorts A and B suggest that the overall procedure is very likely to meet its feasibility goal since 9/10 patients have done so as of the date this amendment was constructed. As a result, the goal of the two new cohorts is to determine in a preliminary fashion if the treatment proposed in each cohort is able to offer clinical benefit to patients. Data on similar patients suggests a median time to progression of approximately 2 months, and approximately 10-15% would have stable disease at 6 months. It would be a very meaningful improvement if the treatment proposed could be associated with results which were consistent with 50% of patients having stable disease at 6 months. With the goal of keeping the trial small, in each cohort of 10 patients the trial will have 82% power to rule out 15% as the proportion stable at 6 months in favor of 50% being stable at 6 months, with each evaluation assuming that a one-sided 0.10 significance level exact binomial test would be performed. As a practical matter, 10 patients will be enrolled in each of the two cohorts and if there are 3 patients in 10 who are able to have stable disease at a 6 month evaluation, then the lower one-sided 90% confidence bound for 3/10 is 11.6% (the two sided 80% confidence interval extends from 11.6% to 55.2%). Similarly, with 4 in 10 with stable disease at 6 months, the lower one-sided 90% confidence bound for 4/10 is 18.8% (the two sided 80% confidence interval extends from 18.8% to 64.6%). Thus, in any given cohort, 3 or 4 patients attaining stable disease at 6 months would rule out 10-15% as the fraction who would do so, with 90% one sided confidence.

With amendment G, cohort E (cholangiocarcinoma patients) will be expanded to a total of 20 patients. This cohort will have 97% power to rule out 15% as the proportion stable at 6 months in favor of 50% being stable at 6 months, with the evaluation assuming that a one-sided 0.10 significance level exact binomial test would be performed. If there are 6 patients in 20 who are

able to have stable disease at a 6 month evaluation, then the lower one-sided 90% confidence bound for 6/20 is 16.6% (the two sided 80% confidence interval extends from 16.6% to 46.7%). Thus, in cohort E, having 6 or greater patients attaining stable disease at 6 months would rule out 15% as the fraction who would do so, with 90% one-sided confidence.

In addition to evaluations of response and 6 month disease stabilization, Kaplan-Meier curves for progression free survival (PFS) will be constructed based on each of cohorts A, B, and E.

8.3 SECONDARY AND EXPLORATORY ANALYSES

In all cohorts, the actual levels of changes of immune parameters will also be determined, and the fractions that are noted to have a change in the parameter values which would be considered immune responses will be reported. These will be considered secondary and exploratory analyses. Exploratory analyses may also be done informally comparing results for those receiving one procedure with another, e.g. RFA vs. TACE. In cohort B, 20 patients are expected to be enrolled (following amendment G); the same types of analyses are anticipated, but will be considered very tentative and hypothesis generating in view of the small numbers of patients to be evaluated.

Safety and toxicity will also be evaluated and addressed by tabulating and monitoring the grades of toxicity experienced by patients in the study.

At the conclusion of the trial, the clinical results and the immune parameter results may be used to arrive at an overall judgment involving which cohort or cohorts may merit expansion or further evaluation in subsequent trials.

8.4 ACCRUAL

It is expected that up to 2 patients per month may be able to enroll onto this trial. Cohort A may theoretically enroll a maximum of 26 evaluable patients at both dose levels combined, and there also may be 20 evaluable patients in cohort B, 10 in cohort D, and 20 in cohort E. The accrual ceiling for the protocol will be set at 90 patients to allow for a small number of inevaluable patients. Thus, it is expected that 48-60 months may be needed to accrue all patients onto this trial.

9 COLLABORATIVE AGREEMENTS

9.1 COOPERATIVE RESEARCH AND DEVELOPMENT AGREEMENT (CRADA)

A CRADA (02853) is in place with MedImmune, Inc. for supply of the investigational agent.

9.2 MATERIAL TRANSFER AGREEMENTS (MTA)

MTA (38376-14) is in place with Hannover Medical School

MTA (40860-16) is in place with Adaptive Biotechnologies

10 HUMAN SUBJECTS PROTECTIONS

10.1 RATIONALE FOR SUBJECT SELECTION

Subjects treated on this study, will be individuals with advanced hepatocellular carcinoma (HCC), which has recurred (or persisted) after appropriate standard treatment. Individuals of any race or ethnic group will be eligible for this study. Eligibility assessment will be based solely on the patient's medical status. Recruitment of patients onto this study will be through standard CCR mechanisms. No special recruitment efforts will be conducted.

10.2 PARTICIPATION OF CHILDREN

Individuals under the age of 18 will not be eligible to participate in this study because they are unlikely to have hepatocellular or biliary tract carcinoma, and because of unknown toxicities in pediatric patients.

10.3 PARTICIPATION OF SUBJECTS UNABLE TO GIVE CONSENT

Adults unable to give consent are excluded from enrolling in the protocol. However, re-consent may be necessary and there is a possibility, though unlikely, that subjects could become decisionally impaired. For this reason and because there is a prospect of direct benefit from research participation (section 10.5), all subjects will be offered the opportunity to fill in their wishes for research and care, and assign a substitute decision maker on the “NIH Advance Directive for Health Care and Medical Research Participation” form so that another person can make decisions about their medical care in the event that they become incapacitated or cognitively impaired during the course of the study. Note: The PI or AI will contact the NIH Ability to Consent Assessment Team for evaluation. For those subjects that become incapacitated and do not have pre-determined substitute decision maker, the procedures described in MEC Policy 87-4 for appointing a surrogate decision maker for adult subjects who are (a) decisionally impaired, and (b) who do not have a legal guardian or durable power of attorney, will be followed.

10.4 EVALUATION OF BENEFITS AND RISKS/DISCOMFORTS

10.4.1 Risks of exposure to ionizing radiation

This research study involves three CT guided biopsies collected for research purposes only. Subjects undergoing three optional biopsy collection will be exposed to 2.3 rem. This amount of radiation is below the guideline of 5 rem per year allowed for adult research subjects by the NIH Radiation Safety Committee.

10.4.2 Risk of optional biopsy

All care will be taken to minimize risks that may be incurred by tumor sampling. However, there are procedure-related risks (such as bleeding, infection and visceral injury) that will be explained fully during informed consent.

10.4.3 Other risks/benefits

The potential benefit to a patient that goes onto study is a reduction in the bulk of their tumor which may or may not have favorable impact on symptoms and/or survival. Potential risks include the possible occurrence of any of a range of side effects which are listed in the Consent Document. The procedure for protecting against or minimizing risks will be to medically evaluate patients on a regular basis as described.

10.5 RISKS/BENEFITS ANALYSIS

For patients with hepatocellular carcinoma and biliary cancer, median survival is in the range of 6 months. It is possible that treatment on this protocol may reduce tumor burden or lessen symptoms caused by the cancer. While treatment on this protocol may not individually benefit subjects. The knowledge gained from this study may help others in the future who have hepatocellular carcinoma. Potential risks include the possible occurrence of any of a range of side effects listed. If patients suffer any physical injury as a result of the biopsies, immediate

medical treatment is available at the NIH's Clinical Center in Bethesda, Maryland. Although no compensation is available, any injury will be fully evaluated and treated in keeping with the benefits or care to which patients are entitled under applicable regulations.

10.6 CONSENT AND ASSENT PROCESS AND DOCUMENTATION

Patients will meet with an associate or principal investigator on the trial in the GI oncology Clinic, during the initial evaluation for this study. During that meeting, the investigator will inform patients of the purpose, alternatives, treatment plan, research objectives and follow-up of this trial. The investigator will then provide a copy of the IRB-approved informed consent document that is included in this protocol. The patient will be allowed to take as much time as he wishes, in deciding whether or not he wishes to participate. If a prolonged period of time expires during the decision making process (several weeks, as an example), it may be necessary to reassess the patient for protocol eligibility. The original signed consent goes to Medical Records; copy placed in research record (NIH policy).

All patients must have a signed informed consent form and an on-study (confirmation of eligibility) form filled out and signed by a participating investigator before entering on the study.

10.6.1 Telephone re-consent

The informed consent document will be sent to the subject. An explanation of the study will be provided over the telephone after the subject has had the opportunity to read the consent form. The subject will sign and date the informed consent. A witness to the subject's signature will sign and date the consent.

The original informed consent document will be sent back to the consenting investigator who will sign and date the consent form with the date the consent was obtained via telephone.

A fully executed copy will be returned via mail for the subject's records.

The informed consent process will be documented on a progress note by the consenting investigator and a copy of the informed consent document and note will be kept in the subject's research record.

10.6.2 Informed consent of non-English speaking subjects

If there is an unexpected enrollment of a research participant for whom there is no translated extant IRB approved consent document, the principal investigator and/or those authorized to obtain informed consent will use the Short Form Oral Consent Process as described in MAS Policy M77-2, OHSRP SOP 12, 45 CFR 46.117 (b) (2), and 21 CFR 50.27 (b) (2)). The summary that will be used is the English version of the extant IRB approved consent document. Signed copies of both the English version of the consent and the translated short form will be given to the subject or their legally authorized representative and the signed original will be filed in the medical record.

Unless the PI is fluent in the prospective subject's language, an interpreter will be present to facilitate the conversation (using either the long translated form or the short form). Preferably someone who is independent of the subject (i.e., not a family member) will assist in presenting information and obtaining consent. Whenever possible, interpreters will be provided copies of the relevant consent documents well before the consent conversation with the subject (24 to 48 hours if possible).

We request prospective IRB approval of the use of the short form process for non-English speaking subjects and will notify the IRB at the time of continuing review of the frequency of the use of the Short Form.

11 PHARMACEUTICAL INFORMATION

11.1 TREMELIMUMAB

Tremelimumab is a human IgG2 anti-CTLA-4 mAb that is being developed as an immunotherapeutic agent for various cancers. Tremelimumab will be supplied by MedImmune.

Investigational Product	Manufacturer	Concentration and Formulation as Supplied
Tremelimumab	MedImmune	Formulated at a nominal concentration of 20 mg/mL in 20 mM histidine/histidine hydrochloride, 222 mM trehalose dihydrate, 0.02% (w/v) polysorbate 80, and 0.27 mM disodium edetate dihydrate (EDTA), pH 5.5.

Tremelimumab is to be administered as an IV solution of 10 mg/kg at a rate of 250 mL/hr, followed by observation for 60 minutes.

11.1.1 Investigational Product Dose Preparation

Tremelimumab is supplied as a sterile IV solution, filled in 20 mL clear glass vials with a rubber stopper and aluminum seal. Each vial contains 20 mg/mL (with a nominal fill of 20 mL accounting to 400 mg/vial) of Tremelimumab, in an isotonic solution at pH 5.5. Vials containing Tremelimumab must be stored in the refrigerator at 2-8°C. The 20 mg/mL solution will be diluted into a saline bag for IV infusion. Vials containing Tremelimumab may be gently inverted for mixing, but should not be shaken.

For dose preparation steps, the following ancillary items are required:

- IV infusion bags of 0.9% sodium chloride injection (250 mL size). Saline bags must be latex-free and can be made of polyvinyl chloride (PVC) or polyolefins (e.g. polyethylene), manufactured with bis (2-ethylhexyl) phthalate (DEHP) or DEHP-free.
- IV infusion lines made of PVC/DEHP or PVC/tri octyl trimellitate (TOTM) or polyethylene or polyurethane. All DEHP-containing or DEHP-free lines are acceptable. Lines should contain a 0.22 or 0.2 µm in-line filter. The in-line filter can be made of

polyethersulfone (PES) or polyvinylidene fluoride DRF (PVDF). Lines containing cellulose-based filters should not be used with Tremelimumab.

- Catheters/infusion sets made of polyurethane or fluoropolymer with silicone and stainless steel and/or PVC components.
- Syringes made of polypropylene and latex-free. Polycarbonate syringes should not be used with Tremelimumab.
- Needles made of stainless steel.

11.1.2 Dose Calculation

The subject's weight (in kilograms) must be measured prior to each dosing for dose calculation. Measurements can be taken in street clothes without shoes and a calibrated scale must be used for all measurements.

The dose will be calculated at each dosing visit using the following formula:

$$\text{Dose (mL)} = \frac{[\text{subject weight (kg)} \times \text{dose level (10 mg/kg)}] \text{ drug concentration (20 mg/mL)}}{20}$$

The corresponding volume of investigational product should be rounded to the nearest tenth of a mL (0.1 mL). Each vial contains a small amount of overage and the overage should be utilized as much as possible before using another vial.

The number of vials required for dose preparation is the next greatest whole number of vials from the following formula: Number of vials = Dose (mL) ÷ 20 (mL/vial)

11.1.3 Investigational Product Inspection

Each vial selected for dose preparation should be inspected.

If there are any defects noted with the investigational product, the investigator and site monitor should be notified immediately. Refer to the Product Complaint section (10.1.6) for further instructions.

During the inspection if the solution is not clear or any turbidity, discoloration or particulates are observed, notify your site monitor and store the vial(s) in QUARANTINE at refrigerated (2-8°C) temperature for drug accountability and potential future inspection.

Notify the IXRS that the unusable vials are damaged. The IXRS will indicate the replacement vials. Select appropriate replacement vials for the preparation of the subject's dose, and perform the same inspection on the newly selected vials. For accountability, record the total number of vials removed from site inventory. Used vials should be held for accountability purposes at ambient storage temperature.

11.1.4 Dose Preparation Steps

Tremelimumab does not contain preservatives and any unused portion must be discarded. Preparation of Tremelimumab and preparation of the IV bag are to be performed aseptically. Total in-use storage time for the prepared final IV bag should not exceed 24 hours at 2-8°C or 4 hours at room temperature (25°C). However, it is recommended that the prepared final IV bag be stored in the dark at 2-8°C until needed. The refrigerated infusion solutions in the prepared final

IV bag should be equilibrated at room temperature for about 2 hours prior to administration. If storage time exceeds these limits, a new dose must be prepared from new vials.

The investigational product manager or qualified personnel will be responsible for preparing the IV doses using the following steps:

- 1) Select the IXRS-assigned number of vials of investigational product required to prepare the subject's dose.
- 2) All investigational product vials should be equilibrated to room temperature for 30 minutes prior to dose preparation.
- 3) To prepare the IV bag, first, calculate the dose volume of investigational product required. Second, remove the volume of 0.9% sodium chloride IV solution equivalent to the calculated dose volume of investigational product from the IV bag. Lastly, add the calculated dose volume of investigational product to the IV bag. Gently mix the solution in the bag by inverting up and down. Avoid shaking the IV bag to prevent foaming.

Example: A subject weighing 85 kg will require 42.5 mL (3 vials) of investigational product. Remove 42.5 mL of saline from the commercial IV bag. Add the 42.5 mL of investigational product to the IV bag and gently mix by inverting up and down.

Tremelimumab should be stored at refrigerated temperatures (2°C to 8°C), and should not be frozen.

Labels will be prepared in accordance with Good Manufacturing Practice (GMP).

11.1.5 Investigational Product Accountability

The investigator's or site's designated investigational product manager is required to maintain accurate investigational product accountability records. Upon completion of the study, copies of investigational product accountability records will be returned to MedImmune. All unused investigational product will be returned to a MedImmune-authorized depot or disposed of upon authorization by MedImmune.

11.1.6 Reporting Product Complaints

Any defects with the investigational product must be reported *immediately* to the MedImmune Product Complaint Department by the site with further notification to the site monitor. All defects will be communicated to MedImmune and investigated further with the Product Complaint Department. During the investigation of the product complaint, all investigational products must be stored at labeled conditions unless otherwise instructed.

Product defects may be related to component, product, or packaging and labeling issues. The list below includes, but is not limited to, descriptions of product complaints that should be reported.

Component Issue: Defect in container or dosing mechanism of the investigational product. The component defect may be damaged, missing, or broken. Component examples include vials, stoppers, caps, spray barrels, spray nozzles, or plungers.

Product Issue: Defect in the product itself. The product appearance has visual imperfections such as foreign particles, crystallization, discoloration, turbidity, insufficient volume, or anything that does not apply to the product description.

Packaging/Labeling Issue: Defect in the packaging or labeling of the product. The packaging or labeling defects may be damaged or unreadable, or the label may be missing.

When reporting a product complaint, site staff must be prepared to provide the following information:

- 1) Customer information: reporter name, address, contact number, and date of complaint
- 2) Product information: product name, packaging kit number or lot number, expiry date, and clinical protocol number
- 3) Complaint information: complaint issue category and description

MedImmune contact information for reporting product complaints:

Email: [contact]

[contact] [name] ([contact])

[contact]

Mail: MedImmune, LLC Attn: Product Complaint Department [name],
[name]

13 APPENDICES

13.1 APPENDIX A: PERFORMANCE STATUS CRITERIA

ECOG Performance Status Scale		Karnofsky Performance Scale	
Grade	Descriptions	Percent	Description
0	Normal activity. Fully active, able to carry on all pre-disease performance without restriction.	100	Normal, no complaints, no evidence of disease.
		90	Able to carry on normal activity; minor signs or symptoms of disease.
1	Symptoms, but ambulatory. Restricted in physically strenuous activity, but ambulatory and able to carry out work of a light or sedentary nature (e.g., light housework, office work).	80	Normal activity with effort; some signs or symptoms of disease.
		70	Cares for self, unable to carry on normal activity or to do active work.
2	In bed <50% of the time. Ambulatory and capable of all self-care, but unable to carry out any work activities. Up and about more than 50% of waking hours.	60	Requires occasional assistance, but is able to care for most of his/her needs.
		50	Requires considerable assistance and frequent medical care.
3	In bed >50% of the time. Capable of only limited self-care, confined to bed or chair more than 50% of waking hours.	40	Disabled, requires special care and assistance.
		30	Severely disabled, hospitalization indicated. Death not imminent.
4	100% bedridden. Completely disabled. Cannot carry on any self-care. Totally confined to bed or chair.	20	Very sick, hospitalization indicated. Death not imminent.
		10	Moribund, fatal processes progressing rapidly.
5	Dead.	0	Dead.

13.2 APPENDIX B: CHILD-PUGH CLASSIFICATION SYSTEM

Parameter	Points assigned		
	1	2	3
Ascites	Absent	Slight	Moderate
Bilirubin	<2 mg/dL (<34.2 micromol/liter)	2-3 mg/dL (34.2 to 51.3 micromol/liter)	>3 mg/dL (>51.3 micromol/liter)
Albumin	>3.5 g/dL (35 g/liter)	2.8-3.5 g/dL (28 to 35 g/liter)	<2.8 g/dL (<28 g/liter)
Prothrombin time			
Seconds over control	<4	4-6	>6
INR	<1.7	1.7-2.3	>2.3
Encephalopathy	None	Grade 1-2	Grade 3-4

Modified Child-Pugh classification of the severity of liver disease according to the degree of ascites, the plasma concentrations of bilirubin and albumin, the prothrombin time, and the degree of encephalopathy. A total score of 5-6 is considered grade A (well-compensated disease); 7-9 is grade B (significant functional compromise); and 10-15 is grade C (decompensated disease). These grades correlate with one- and two-year patient survival: grade A - 100 and 85 percent; grade B - 80 and 60 percent; and grade C - 45 and 35 percent.

13.3 APPENDIX C: MODIFIED IMMUNE-RELATED RESPONSE CRITERIA (irRC)

This new classification is based on the recent learning from clinical studies with cancer immunotherapies that even if some new lesions appear at the beginning of a treatment or if the total tumor burden does not increase substantially, tumor regressions or stabilizations might still occur later. The irRC were created using bi-dimensional measurements (as previously widely used in the World Health Organization criteria). For this trial, the concepts of the irRC are combined with RECIST 1.1 to come up with the modified irRC.

For modified irRC, only target and measurable lesions are taken into account. In contrast to the RECIST 1.1 criteria, the modified irRC criteria (a) require confirmation of both progression and response by imaging at 6 weeks after initial imaging and (b) do not necessarily score the appearance of new lesions as progressive disease if the sum of lesion diameters of target lesions (minimum of 10 mm per lesion, maximum of 5 target lesions, maximum of 2 per organ) and measurable new lesions does not increase by $\geq 20\%$.

The same method of assessment and the same technique should be used to characterize each identified and reported target lesion(s) at baseline, during the trial, and at the end of trial visit. All measurements should be recorded in metric notation. The modified irRC based on RECIST 1.1 are displayed below.

Modified immune-related response criteria are defined as follows:

New measurable lesions: Incorporated into tumor burden.

New non-measurable lesions: Do not define progression but precludes (irCR).

Overall irCR: Complete disappearance of all lesions (whether measurable or not) and no new lesions. All measurable lymph nodes also must have a reduction in short axis to 10 mm.

Overall irPR: Sum of the longest diameters of target and new measurable lesions decreases $\geq 30\%$.

Overall irSD: Sum of the longest diameters of target and new measurable lesions neither irCR, irPR, (compared to baseline) or irPD (compared to nadir).

Overall irPD: Sum of the longest diameters of target and new measurable lesions increases $\geq 20\%$ (compared to nadir), confirmed by a repeat, consecutive observations at least 4 weeks (normally it should be done at 6 weeks) from the date first documented.

Overall Responses Derived from Changes in Index, Non-Index, and New Lesions

Measurable Response	Non-Measurable Response		Overall Response Using Modified irRC
	Non-Index Lesions	New, Non-Measurable Lesions	
Index and New, Measurable Lesions (Tumor Burden) ¹			
Decrease 100%	Absent	Absent	irCR ²
Decrease 100%	Stable	Any	irPR ²
Decrease 100%	Unequivocal progression	Any	irPR ²
Decrease \geq 30%	Absent / Stable	Any	irPR ²
Decrease \geq 30%	Unequivocal progression	Any	irPR ²
Decrease < 30% to increase < 20%	Absent / Stable	Any	irSD
Decrease < 30% to increase < 20%	Unequivocal progression	Any	irSD
Increase \geq 20%	Any	Any	irPD

¹ Decreases assessed relative to baseline

² Assuming that the response (irCR and irPR) and progression (irPD) are confirmed by a second, consecutive assessment at least 4 weeks apart (normally it should be done 6 weeks apart).

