3.12 CRITERIA FOR REMOVAL FROM PROTOCOL THERAPY AND OFF STUDY CRITERIA

3.12.1 Criteria for removal from protocol therapy

Prior to removal from the study, effort must be made to have all subjects complete a safety visit approximately 30 days following the last dose of study therapy

In the absence of treatment delays due to adverse events, treatment may continue until one of the following criteria applies:

- Disease progression (per immune-related response criteria)
- Completion of 2 years' protocol therapy with tremelimumab
- Intercurrent illness that prevents further administration of treatment
- Unacceptable adverse event(s)
- Participant requests to be withdrawn from active therapy
- Investigator discretion
- Positive pregnancy test
- Delayed recovery from toxicity that prevents re-treatment in ≤ 28 days of scheduled therapy
- Completed end of treatment safety visit

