6.3.4 Response Criteria

6.3.4.1 Evaluation of Target Lesions

Complete Response (CR): Disappearance of all target lesions. Any pathological lymph nodes (whether target or non-target) must have reduction in short axis to <10 mm.

Partial Response (PR): At least a 30% decrease in the sum of the diameters of target lesions, taking as reference the baseline sum of diameters.

Progressive Disease (PD): At least a 20% increase in the sum of the diameters of target lesions, taking as reference the smallest sum on study (this includes the baseline sum if that is the smallest on study). In addition to the relative increase of 20%, the sum must also demonstrate an absolute increase of at least 5 mm. (Note: the appearance of one or more new lesions is also considered progressions).

Stable Disease (SD): Neither sufficient shrinkage to qualify for PR nor sufficient increase to qualify for PD, taking as reference the smallest sum of diameters while on study.

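### The modified irRC define progression by a 20% increase alone, without the 5 mm absolute increase that the RECIST section requires, so for nadir sums below 25 mm measurement error can be recorded as confirmed irPD

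*Combined protocol and SAP*

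**What the plan says.** For RECIST, section 6.3.4.1 sets progression at 20% over the smallest sum on study and adds: "In addition to the relative increase of 20%, the sum must also demonstrate an absolute increase of at least 5 mm".

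Appendix C (section 13.3) states the immune-related rule as "Overall irPD: Sum of the longest diameters of target and new measurable lesions increases" by 20% or more ("compared to nadir), confirmed by a repeat, consecutive observations at least 4 weeks" after the increase is first seen). Its table follows suit. The irSD rows run "Decrease < 30% to increase < 20" per cent, the irPD row starts at 20%, and the footnote applies if response and "progression (irPD) are confirmed by a second, consecutive assessment at least 4 weeks apart". Neither the definition nor the table contains a condition in millimetres.

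The appendix describes its criteria as based on RECIST 1.1 and lists the differences: "In contrast to the RECIST 1.1 criteria, the modified irRC criteria (a) require confirmation of both progression and response by imaging at 6 weeks", and (b) new lesions are not automatically progression. Removal of the absolute floor is not listed. Target lesions are limited to a "minimum of 10 mm per lesion, maximum of 5 target lesions, maximum of 2 per organ", so a single 10 mm lesion is a permitted baseline sum.

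Section 3.2 gives time to progression as the purpose of the 8-weekly scans and says that both systems will be used; time to progression is a secondary endpoint in 1.1.2. Section 3.12.1 lists "Disease progression (per immune-related response criteria") as a reason for stopping protocol therapy, and sections 2.1.3 and 3.3.4 make re-induction depend on immune-related progression.

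**The concern.** A purely relative threshold becomes a very small distance when the sum is small. The absolute condition in 6.3.4.1 prevents a change of a few millimetres from counting as progression. Without it, an unchanged small tumour can reach irPD through reading variation alone, and the irRC time to progression is then too short. Because the reference is the nadir, a patient can also enter the affected range through shrinkage on treatment.

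The text is also ambiguous. A reader who takes the appendix as RECIST 1.1 with two named changes would keep the floor; a reader who applies the written definition would not. The same scans could be classed as irSD by one and irPD by the other.

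**Working it through.** The plan gives no figure that depends on this point, so there is none to reproduce.

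**Inputs from the documents.** Relative threshold 20% over nadir (6.3.4.1 and 13.3); absolute floor 5 mm (6.3.4.1 only); confirmation at least 4 weeks later (13.3 only); smallest target lesion 10 mm (13.3); scans every 8 weeks (3.2, 6.3), hence weeks 8, 16 and 24 by about 6 months.

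**Assumption.** The documents give no measurement error. The SD per lesion was varied over 0.5, 1, 1.5 and 2 mm, with 3 mm as an extreme.

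**Step 1: where the rules differ.** The floor matters only if 0.20 × nadir < 5 mm, that is, nadir < 5 / 0.20 = 25 mm. The band in which irPD and RECIST disagree on target lesions runs from 0.20 × nadir up to 5 mm: 2 to 5 mm at a nadir of 10 mm, 3 to 5 mm at 15 mm, 4 to 5 mm at 20 mm, 4.8 to 5 mm at 24 mm. Example: from 15 to 18.5 mm is +3.5 mm, or 3.5 / 15 = 23.3%. Once confirmed this is irPD; by 6.3.4.1 it is stable disease.

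**Step 2: false confirmed irPD when nothing has changed.** Each measured value is the true sum plus independent normal error. The nadir is the running minimum, starting from baseline. A scan is called if it is at least 1.2 × nadir (with the floor, also at least nadir + 5 mm). It is confirmed if one repeat scan meets the same condition against the same nadir. There were 400,000 runs per cell. One target lesion, by about 6 months, without floor / with floor, in per cent:

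| True sum | SD 0.5 mm | SD 1 mm | SD 1.5 mm | SD 2 mm |
|---|---|---|---|---|
| 10 mm | 0.4 / 0.0 | 17.1 / 0.0 | 37.4 / 0.6 | 50.7 / 4.3 |
| 15 mm | 0.0 / 0.0 | 3.5 / 0.0 | 17.1 / 0.6 | 31.5 / 4.4 |
| 20 mm | 0.0 / 0.0 | 0.4 / 0.0 | 6.2 / 0.6 | 17.0 / 4.3 |
| 24 mm | 0.0 / 0.0 | 0.1 / 0.0 | 2.3 / 0.6 | 9.6 / 4.3 |
| 30 mm | 0.0 / 0.0 | 0.0 / 0.0 | 0.4 / 0.4 | 3.4 / 3.4 |

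Confirmation already removes many false calls: at 10 mm and SD 1 mm, 37.3% have a first call and 17.1% a confirmed one.

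The floor is not a complete cure. At SD 3 mm and 10 mm the rate is 65.0% without it and 18.8% with it. For two lesions totalling 20 mm at SD 2 mm per lesion, it is 34.4% and 16.1%.

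**Step 3: against RECIST as the protocol writes it.** RECIST progression has the floor but needs no confirmation. Confirmed irPD without floor versus unconfirmed RECIST progression, same simulation:

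| True sum | SD 1.5 mm | SD 2 mm |
|---|---|---|
| 10 mm | 37.4% v 4.7% | 50.7% v 17.1% |
| 15 mm | 17.1% v 4.6% | 31.5% v 17.0% |
| 20 mm | 6.2% v 4.6% | 17.0% v 17.0% |
| 24 mm | 2.3% v 4.6% | 9.6% v 17.0% |

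The irPD rule gives clearly more false calls at 10 to 15 mm, about the same at 20 mm, and fewer at 24 mm.

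**The case against.** The best reply is that the appendix builds on RECIST 1.1, so the floor may have been meant to carry over, and that confirmation already guards against reading error. The first part shows that the omission may be unintended, but the written definition and table still lack the condition. The second part is largely right near 20 to 24 mm and fails at 10 to 15 mm unless the SD is well below 1 to 1.5 mm.

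Several stronger readings are tempting and are not supported:

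- A reader might infer that ordinary measurement error generally becomes confirmed irPD. The rate runs from nearly nil to about one half, depending on an SD and a sum size that the documents do not give.
- A reader might infer that irRC is the stricter system overall. Step 3 contradicts this near 20 to 24 mm. The modified irRC also do not let non-target progression or a new lesion alone define progression, whereas 6.3.4.2 and 6.3.4.3 do.
- A reader might infer that small sums are expected, from the 1 to 5 cm range in Table 1 (section 1.2.1). That range is the indication for potentially curative RFA, and patients amenable to curative ablation are excluded. Up to five targets are allowed, chosen by size, and no distribution of sums is given. For the same reason, it is not shown that the best responders are hit hardest.
- A reader might infer that the 6-month stable-disease rate is biased. Section 8 does not say which criteria define it, and section 6.3 assigns response and progression to RECIST 1.1, which has the floor. The power figures and decision rules do not depend on this point.

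**Conclusion.** The inconsistency is certain: 6.3.4.1 requires a 5 mm increase, Appendix C does not, and Appendix C does not declare the difference. Applied as written, the irPD rule can class a confirmed change of under 5 mm as progression when the nadir sum is below 25 mm, and irRC time to progression is the endpoint exposed. The size rests on the assumed SD, an unchanged single lesion, normal independent errors and three scans; scanning continues after week 24, so the chance accumulates. The number of patients affected cannot be stated, because the documents permit small sums without saying how common they are. This is a faulty stated rule that is worth correcting; it is not evidence that the trial's main efficacy analysis is wrong.

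**What to change.** For irRC endpoint classification (irRC response and irRC time to progression), add to the irPD definition in Appendix C, and to the table row for an increase of 20% or more, that the sum must also rise by at least 5 mm over nadir. Change the irSD rows to match, so that a rise of 20% or more but under 5 mm falls there. State that the clause governs endpoint classification.

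Sections 3.12.1, 2.1.3 and 3.3.4 use immune-related progression for removal from therapy and re-induction. There the two definitions of progression must be reconciled and the intended one stated; which clinical rule to apply is for the sponsor and investigators, and none is proposed here.

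The cost is one clause and a table edit. The measurements are already collected, so existing scans can be reclassified. The small downside is that a true progression of under 5 mm in a small tumour is called later.
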